294 order to randomize a minimum of 72 participants.

295

296 As the randomization goal approaches attainment, sites will be notified of the end date for
297 recruitment into the study. Participants who have signed informed consent forms are enrolled and
298 can be randomized until the end date, which means the expected recruitment number might be
299 exceeded. The maximum number randomized will be 82.

300

301 There is no restriction on the number of participants to be enrolled by each site toward the
302 overall recruitment goal. The overall number of participants with an interocular difference in
303 distance VA of 2 logMAR lines (10 letters on E-ETDRS for patients ≥ 7 years old) will be
304 limited to 14.

305

306 **2.1.1 Informed Consent**

307 Children with IXT who are 3 to <9 years of age attending ophthalmology or optometry
308 outpatient visits will be identified.

309

310 Families who qualify for the study will be approached by one of the research team members. The
311 study will be discussed with the child's parent(s) or guardian(s) [referred to subsequently as
312 parent(s)]. Parent(s) who express an interest in the study will be given a copy of the informed
313 consent form to read. Written informed consent must be obtained from a parent and written or
314 verbal assent from the child (depending on age and local IRB requirements) prior to performing
315 any study-specific procedures that are not part of the child's routine care.

316

317 A child is considered enrolled into the study when the informed consent form has been signed by
318 the parent, the assent form has been signed by the child (when applicable), and the investigator
319 has also signed the appropriate forms.

320

321 **2.2 Eligibility Criteria**

322 **2.2.1 Inclusion Criteria**

323 Children under the care of a pediatric optometrist or pediatric ophthalmologist, who are
324 identified during a standard-of-care outpatient visit or from a referral from another provider, will
325 be eligible for the study if they meet all the following criteria:

326

1. Age 3 to <9 years

327

2. IXT meeting all the following criteria:

328

- Intermittent or constant XT at distance (mean distance control 2.0 or more) with at least 1 measure of 3, 4 or 5 (i.e., indicating spontaneous tropia) on control testing

329

- Either IXT, exophoria, or orthophoria at near (cannot have control score of 5 on all 3 near assessments)

330

- Distance exodeviation between 15Δ and 50Δ by PACT

331

- Near exodeviation between 0Δ and 50Δ by PACT

332

- Near exodeviation does not exceed distance by more than 10Δ by PACT

333

334

3. Age-normal visual acuity in both eyes:⁵⁶⁻⁵⁸

335

- 336
- 337
- 338
- 339
- 340
- 341
- 342
- 343
- 344
- 345
- 346
- 347
- 348
- 349
- 350
- 351
- 352
- 353
- 354
- 355
- 356
- 357
- 358
- 359
- 360
- 361
- 362
- 363
- 364
- 365
- 366
- 367
- 368
- 369
- 370
- 371
- 372
- 373
- 374
- 375
- 376
- 377
- 378
- 379
- 380
- 381
- 3 years: 20/50 or better (≥ 63 letters)
 - 4 years: 20/40 or better (≥ 68 letters)
 - 5-6 years: 20/32 or better (≥ 73 letters)
 - 7-<9 years: 20/25 or better (≥ 78 letters)
4. Interocular difference in distance VA of 2 logMAR lines or less (10 letters or less on E-ETDRS for patients ≥ 7 years old). Testing by ATS HOTV for participants 3 to < 7 years old and by E-ETDRS for participants ≥ 7 years old.
 - The overall number of participants with an interocular difference in distance VA of 2 logMAR lines (10 letters on E-ETDRS for patients ≥ 7 years old) will be limited to 14.
 5. Refractive error between -6.00 D SE and +2.00 D SE (inclusive) based on cycloplegic refraction performed within 7 months
 6. Participants with refractive error meeting any of the following based on cycloplegic refraction performed within the prior 7 months must be wearing spectacles for at least 2 weeks:
 - Myopia > -0.50 D spherical equivalent (SE) in either eye
 - Anisometropia > 1.00 D SE
 - Astigmatism in either eye > 1.00 D
 7. Any refractive correction worn at enrollment (required or not) must meet the following guidelines based on cycloplegic refraction performed within the prior 7 months:
 - Anisometropia SE must be within 0.50 D of the full anisometropic difference correction
 - Astigmatism must be corrected within 0.50 D
 - Axis must be within ± 10 degrees if cylinder power is ≤ 1.00 D and within ± 5 degrees if cylinder power is > 1.00 D.
 - For hyperopia, the spherical component can be reduced at investigator discretion provided the reduction is symmetrical and does not meet the definition of deliberate overminus (see below).
 - For refractive errors with an emmetropic or myopic SE, the intent is to fully correct, but the spherical component can be undercorrected at investigator discretion provided the reduction is symmetrical and results in no more than -0.50 D SE residual (i.e., uncorrected) myopia. Deliberate overminus is not allowed.
 - Deliberate overminus is defined for this protocol as any refractive correction prescribed to yield lenses that are overminused by more than -0.50D SE than cycloplegic refraction SE.
 - Less than the full cycloplegic hyperopic correction (i.e., prescribing reduced plus) or no correction for a hyperopic SE refractive error is not considered the same as overminusing for this protocol (because most patients without IXT but with hyperopic SE refractions up to +2.00 D SE would not typically be prescribed a refractive correction.)
 - Note that the refractive correction guidelines and the requirement to wear refractive correction for at least 2 weeks apply not only to participants who require refractive correction under the above criteria but also to any other participant who is wearing refractive correction.
 8. Gestational age > 30 weeks

- 382 9. Birth weight > 1500 grams
383 10. Patient and/or parent understands protocol, is willing to enroll, and is willing to accept
384 that other treatment for IXT will not be offered for 3 months
385 11. Parent has phone and is willing to be contacted by Jaeb Center staff
386 12. Relocation outside of area of an active PEDIG site within next 3 months not anticipated
387

388 **2.2.2 Exclusion Criteria**

389 Individuals meeting any of the following criteria at baseline will be excluded from study
390 participation.

- 391 1. Prior strabismus, intraocular, or refractive surgery (including BOTOX injection)
392 2. Prior nonsurgical treatment for IXT (e.g., patching, vergence therapy, vision
393 therapy/orthoptics, base-in prism, or deliberate overminus with spectacles more than
394 1.00 D) for >1 week duration within the past 1 year
395 3. Previous amblyopia treatment other than refractive correction
396 4. Diplopia more than 2 times per day by parental assessment
397 5. Paretic or restrictive strabismus
398 6. Craniofacial malformations affecting the orbits
399 7. Ocular disorders which would reduce VA (except refractive error)
400 8. Severe developmental delay that would interfere with treatment or evaluation (in the
401 opinion of the investigator). Participants with mild speech delay or reading and/or
402 learning disabilities or ADHD are not excluded.
403 9. Neurological anomaly that could affect ocular motility (e.g., cerebral palsy, Down
404 syndrome)
405 10. Immediate family member (child or sibling) of any investigative site personnel directly
406 affiliated with this study.
407 11. Known allergy to adhesive patches.
408 12. Known allergy to silicone.
409

410 **2.3 Historical Information**

411 Historical information elicited will include the following: date of birth, sex, race, ethnicity,
412 spectacle correction, and prior treatment for IXT and amblyopia.
413

414 **2.4 Screening and Baseline Procedures**

415 Testing will be done in the order specified below on a single day following enrollment in the
416 child's current refractive correction if worn (any spectacle correction worn must meet the criteria
417 specified in section 2.2) and without cycloplegia:

- 418 1. Eye-Related Quality of life: Pediatric Eye Questionnaire (PedEyeQ)
419 • Child questionnaire: Completed by children 5 years and older
420 • Parent questionnaire: Completed by the parent for all children regardless of age
421 (includes parent and proxy questions)
422 2. Symptom Survey:
423 • Intermittent Exotropia Symptom Survey completed by children 5 years or older.
424 • Single diplopia question to be completed by children 3 or 4 years.

- 425 3. Diplopia Assessment by Parent: Assess diplopia presence and frequency over the last week,
426 by parental report. If present, classify diplopia frequency as “2 times or less per day” or
427 “more than 2 times per day.”
- 428 4. Monocular Distance VA Testing: Distance VA testing will be performed by a certified
429 examiner on a certified VA system (EVA or M&S), using the ATS single surround HOTV
430 for participants 3 to <7 years old and using the E-ETDRS for participants ≥ 7 years. The
431 same VA testing method used at enrollment will be used again at 3 months.
- 432 5. Stereoacuity Testing: Assessed using the Randot Preschool Stereotest at near (performed at
433 40 cm) as outlined the *IXT7 Procedures Manual*
- 434 6. Control of the Exodeviation #1: Control of the exodeviation at distance (6 meters) then near
435 (1/3 meter) will be assessed using the standardized IXT control scale,³⁵ as outlined in the
436 *IXT7 Procedures Manual*.
- 437 • Testing must be performed by a pediatric ophthalmologist, pediatric optometrist, or
438 certified orthoptist.
 - 439 • The same examiner must assess control for all three assessments of control at each
440 visit.
- 441 8. Divergence Amplitude Testing: Measured at distance (6 meters) using the PEDIG-approved
442 prism bar as described in the *IXT7 Procedures Manual*
- 443 • Testing must be performed by a pediatric ophthalmologist, pediatric optometrist, or
444 certified orthoptist.
 - 445 • Record the break and recovery points.
- 446 9. Convergence Amplitude Testing: Measured at distance (6 meters) using the PEDIG-approved
447 prism bar as described in the *IXT7 Procedures Manual*
- 448 • Testing must be performed by a pediatric ophthalmologist, pediatric optometrist, or
449 certified orthoptist.
- 450 10. Control of the Exodeviation #2 (repeat) (*see item #7*).
- 451 11. Ocular Alignment Testing:
- 452 • Testing must be performed by a pediatric ophthalmologist, pediatric optometrist, or
453 certified orthoptist.
 - 454 • Ocular alignment will be assessed by the cover/uncover test, simultaneous prism and
455 cover test (SPCT), and prism and alternate cover test (PACT) in primary gaze at
456 distance (3 meters) and near (1/3 meter) as described in the *IXT7 Procedures Manual*.
- 457 12. Control of the Exodeviation #3 (repeat) (*see item #7*)
- 458 13. Suppression: Assessment of suppression at distance (6 meters) using the Office Suppression
459 Test⁵⁹ as described in the *IXT7 Procedures Manual*
- 460 • Testing must be performed by a pediatric ophthalmologist, pediatric optometrist, or
461 certified orthoptist.
- 462 14. Retinal Correspondence (children 6 to <9 years only): Assessment of retinal correspondence
463 will be made when aligned and also when tropic using the Hering-Bielschowsky After Image
464 Test⁶⁰ as described in the *IXT7 Procedures Manual* using the PEDIG-supplied flash unit.
- 465 • Testing must be performed by a pediatric ophthalmologist, pediatric optometrist, or
466 certified orthoptist.
- 467

468 **2.5 Randomization**

469 Eligible participants will be randomly assigned on the study website to the following treatment:

470

- 471 1. Observation for 3 months – no treatment other than refractive correction
472 2. Full-time patching (all waking hours) for 3 months (right eye on even days, left eye on odd
473 days), in addition to refractive correction

474

475 The Jaeb Center will construct a Master Randomization List stratified by mean distance control
476 score at enrollment (2 to <3, 3 to <4, 4 to 5). A participant is officially randomized when the
477 website randomization process is completed.

478 **2.5.1 Observation Group**

479 Participants randomized to observation alone will not be allowed to receive any other treatment
480 for IXT, except refractive correction, for 3 months.

481 **2.5.2 Full-Time Patching Group**

482 Participants randomized to the full-time patching group will patch full-time (all waking hours)
483 for 3 months up until the day before the 3-month primary outcome visit. Daily alternate patching
484 will be prescribed (right eye on even days, left eye on odd days). No other treatment for IXT will
485 be used, except for refractive correction.

486 **2.6 Monitoring of Adherence**

487 Site staff will activate and distribute occlusion dose monitors (ODMs) for participants
488 randomized to patching (patching adherence is not applicable to the observation group).

- 489 • Adherence with patching will be monitored throughout the study by an ODM worn on the
490 inside of the patch for participants randomized to patching.
491 • In addition, parents will be asked to record patching wear time and which eye was
492 patched on a study calendar.

493

Chapter 3: Study Follow-up

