199 Previous studies^{22,23,32,33,39,48-50} have shown that the magnitude of the deviation may reduce with
 200 patching treatment. Nevertheless, there are few data that support this notion, and the mechanism
 201 by which patching might alter ocular alignment remains unclear.

202 **1.5 Measuring Patch Wear Time**

203 Adherence with a prescribed patching dose is often problematic and limits the interpretation of
 204 findings when attempting to correlate dose to outcome. In studies of patching treatment for
 205 amblyopia, some research groups have used occlusion dose monitors (ODMs) to record actual
 206 patch wear time.⁵¹⁻⁵⁴ In general these previous studies concluded that dose is a significant factor
 207 in determining amblyopia treatment outcome, although there remains considerable individual
 208 variability. We are unaware of previous studies that have analyzed actual patch wear time when
 209 treating IXT, and such data are important for understanding whether there is a dose effect
 210 relationship.

211 Recently, a new method of monitoring patching adherence has become available and is being
 212 used in a concurrent PEDIG amblyopia study (ATS22, NCT04378790). TheraMon®, a

213 thermosensor device, appears to work well for monitoring adherence with amblyopia patching
 214 treatments in children.⁵¹ We propose utilizing the TheraMon® in the current study to enable
 215 important secondary analyses of outcome in relation to actual (rather than prescribed) wear time.
 216

217 **1.6 Unanswered Questions Regarding Patching Treatment for IXT**

218 While previous data confirm an effect of patching on control of IXT, and even on angle of
 219 deviation, there remain many unanswered questions regarding treatment effectiveness. Such
 220 questions include:

- 221 - Is prescribed full-time patching more effective for improving control and/or reducing
 222 angle of deviation than observation alone?
- 223 - Does patching alter suppression, angle of deviation, fusional amplitudes, or
 224 anomalous retinal correspondence, and are such changes related to exodeviation
 225 control?
- 226 - Is there a dose-response relationship (greater improvement with more actual patching
 227 time)?
- 228 - Which clinical and demographic characteristics, if any, are associated with
 229 improvement in exodeviation control and/or treatment success?

230 **1.7 Rationale for Present Study**

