7.3 Sample Size

Sample size estimation is based on data from our previous IXT2 randomized trial comparing observation versus part-time patching for intermittent exotropia, limited to 278 participants with similar baseline age (3 to <9 years) and baseline control score at distance (2 or higher).²² Data are summarized in Table 1 below.

845 **Table 1 – Previous IXT2 Randomized Trial Data in 3- to <9-Year-Olds with IXT***

	Cohort	
	IXT2 Glasses Alone (Observation)	IXT2 Part-time Patching (3 hours/Day)
Distance Control Scores**		
Baseline		
n	147	131
Mean (SD)	2.88 (1.01)	2.93 (1.00)
3-Month Score		
n	131	116
Mean Score (SD)	2.59 (1.35)	2.15 (1.23)
95% CI for Mean Score	2.35 to 2.82	1.92 to 2.37
95% CI for SD Score	1.21 to 1.54	1.09 to 1.41
3-Month Change from Baseline		
n	131	116
Mean Change (SD)	0.30 (1.23)	0.78 (1.38)
95% CI for Mean Change	0.09 to 0.51	0.53 to 1.04
95% CI for SD Change	1.09 to 1.40	1.22 to 1.59

846 *Participants aged 3 to <9 years old with baseline distance control score of 2 or higher (worse).

847 ** A single measure of control was obtained at each visit in the IXT2 study.

848
849

850 In IXT2, after 3 months of observation versus treatment with 3 hours per day patching, the
851 observation group had a mean change based upon a single measure of distance control of 0.30
852 points (95% CI, 0.09 to 0.51 points) with a standard deviation of 1.23 points (95% CI, 1.09 to
853 1.40 points); and the 3 hours per day patching group had a mean change based upon a single
854 measure of distance control of 0.78 points (95% CI, 0.53 to 1.04 points) with a standard
855 deviation of 1.38 points (95% CI, 1.22 to 1.59 points); group difference patching – observation =
856 0.49 (95% CI 0.16 to 0.81). The correlation between distance control score at baseline and
857 change from baseline after 3 months was R=0.39 (95% CI, 0.27 to 0.48).

858 We are aware of no previous data on distance control score among children with IXT treated
859 with full-time patching. In our IXT5 study, after 6 months of treatment with overminus
860 spectacles, the mean change in distance control was 1.40 points (95% CI, 1.18 to 1.63 points)
861 with a standard deviation of 1.48 points (95% CI, 1.34 to 1.66 points). There was no 3-month
862 outcome in the IXT5 study; however, in the IXT3 pilot study, those treated with overminus
863 spectacles improved on average 1.2 points (95% CI, 0.5 to 1.9 points) with a standard deviation

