864 of 1.8 points (95% CI, 1.4 to 2.5 points) after 8 weeks. Therefore, we estimate that a mean
865 change of 1.45 points after 3 months of full-time patching in the current study is reasonable for
866 an active treatment.

867 **Sample Size Estimation:**

868 The study will be powered for the primary objective.

869 Assuming a mean change in distance control score after 3 months of 0.30 points in the
870 observation group and 1.45 points in the full-time patching group; we estimate that the true
871 difference is 1.15 points between full-time patching and observation at 3 months.

872

873 **Hypothesis Test for Objective – FT vs OBS at 3 Months:**

874 Assuming a pooled standard deviation of 1.5 points for change in distance control score after 3
 875 months, and a correlation of 0.30 between distance control score at baseline and change from
 876 baseline after 3 months, a total sample size of 68 participants (34 per group) completing the 3-
 877 month outcome has 90% power with a type I error rate of 5% to evaluate whether there is a
 878 treatment group difference between FT patching and OBS if the true difference is 1.15 points,
 879 Table 2. Accounting for 5% loss to follow-up after 3 months, a total of 72 participants (36 per
 880 treatment group) will need to be enrolled. The overall number of participants with an interocular
 881 difference in distance VA of 2 logMAR lines (10 letters on E-ETDRS for patients ≥ 7 years old) will be
 882 limited to 14.

883 **Table 2: Total Sample Size for Difference in Mean Distance Control Score**

Standard Deviation of Change in Distance Control (points)	Treatment Group Difference for Outcome of Mean Change in Distance Control (points)		
	0.85	1.00	1.15
1.4	106	78	60
1.5	122	90	68
1.6	138	100	78

884 Cells indicate N for the overall study (two treatment groups combined with a ratio of 1:1), using a 2-sided test with
 885 alpha 0.05, from an analysis of covariance model evaluating a difference between treatment groups for mean change
 886 from baseline in distance control, controlling for baseline distance control.

887

888 If the true effect with FT patching is as small as 0.99, the study would still have 80% power to
 889 reject the null in favor of a difference (and 1.05 with 85%).

890 **7.4 Interim Monitoring**

891 Given the short duration of the primary outcome at 3 months, there will be no formal interim
 892 analysis for stopping the study early for efficacy or futility.

893 **7.5 Analysis Datasets**

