986 The distribution of actual patch wear time will be tabulated overall and by treatment groups. The
987 potential correlation between actual patch wear time in the FT patching group and the change
988 from baseline in the following outcomes will be evaluated at 3 months (when collected):

- 989 1. Distance control score
- 990 2. Near control score
- 991 3. Distance angle of deviation
- 992 4. Near angle of deviation
- 993 5. Level of suppression
- 994 6. Convergence fusional amplitudes
- 995 7. Divergence fusional amplitudes
- 996 8. Symptom survey score
- 997 9. Diplopia assessment by Parent
- 998 10. PedEyeQ score (each domain)

999 A Spearman correlation coefficient and 95% confidence interval will be calculated for each
1000 outcome.

1001 **7.8.2 Outcome of Retinal Correspondence Testing**

1002 The relationship of retinal correspondence response with respect to the following outcomes
1003 within each treatment group will be evaluated at 3 months:

- 1004 1. Distance control score
- 1005 2. Near control score
- 1006 3. Distance angle of deviation
- 1007 4. Near angle of deviation
- 1008 5. Level of suppression
- 1009 6. Convergence fusional amplitudes
- 1010 7. Divergence fusional amplitudes
- 1011 8. Symptom survey score
- 1012 9. Diplopia assessment by Parent
- 1013 10. PedEyeQ score

1014 For continuous outcome variables, the difference in means between participants with normal
1015 versus anomalous retinal correspondence will be calculated along with a 95% confidence
1016 interval. For categorical outcome variables, the difference in proportions between participants
1017 with normal versus anomalous retinal correspondence will be calculated along with a 95%
1018 confidence interval.

1019 **7.8.3 Subgroup Analysis of Distance Control**

1020 The treatment group comparison of distance control will be assessed at 3 months in subgroups
 1021 based on gender and race/ethnicity in accordance with NIH guidelines; however, no effect
 1022 modification is expected for these factors.
 1023

1024 **7.9 Safety Analyses**

1025

1026 **7.9.1 Deterioration**

1027 The number and proportion of participants with deterioration, as defined below, will be tabulated
 1028 for each treatment group at 3 months as a safety outcome.

1029 Deterioration is defined as meeting one of the following criteria at the 3 months follow-up visit:
 1030

- 1031 1. Constant exotropia at least 10Δ at distance **AND** near by SPCT:

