3.3 Level of Suppression

- The proportion with each level of suppression (negligible, mild, moderate, or dense, as indicated on the
- completed follow-up worksheet) by treatment group at 3 months will be tabulated. The median and
- interquartile range for each group will be calculated and the distributions of suppression levels compared

between treatment groups at 3 months using the exact non-parametric Wilcoxon rank-sum test and twosample Hodges-Lehmann estimator.

4 Exploratory Analyses

Exploratory analyses will describe the distribution of the outcome, or change in outcome from baseline, within each treatment group and estimate treatment group differences and 95% confidence intervals (CIs), unless specified otherwise, with the purpose of identifying hypotheses for further study. All exploratory analyses will use observed data only without imputation for missing data. Only visits occurring within the analysis window will be included. As these are exploratory analyses, no adjustment for multiplicity will be made to confidence intervals and no p-values will be reported.

Continuous outcomes will be described using mean, standard deviation, and 95% CIs. Median and interquartile range (IQR) will also be reported if the outcome distribution is asymmetric. Treatment group differences and 95% CIs will be estimated using an ANCOVA model with adjustment for baseline level of the outcome. ANCOVA is relatively robust to violations of normality and homoscedasticity⁴; however, if ANCOVA model estimation of treatment group differences is of questionable validity due to violation of normality or other assumptions, actions to mitigate the violation will be undertaken. For example, for homoscedasticity violations, an ANCOVA model allowing the treatment groups to have different variances may be used and/or large outliers may be winsorized to the 5th and 95th percentiles of the overall outcome distribution (with treatment groups combined). In cases where winsorization of outliers is used, descriptive statistics for the treatment groups will be based on the outcome distribution after winsorization, and winsorized values will be noted in table/figure footnotes. Results of mitigated and original analyses will be compared for consistency, and results of both analyses reported if there are substantial differences.

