262263264

Scatterplots, with Spearman correlation coefficients and 95% confidence intervals, will be generated to illustrate the relationship between the total number of hours patched and each outcome listed below for those with ODM data:

265266

- 267 1. Distance control score
- 268 2. Near control score
- 269 3. Distance angle of deviation
- 270 4. Near angle of deviation
- 5. Suppression Score (0=negligible, 1=mild, 2=moderate, 3=dense)
 - 6. Convergence fusional amplitudes
- 273 7. Divergence fusional amplitudes
 - 8. Symptom Survey Score
 - 9. PedEyeQ score (each domain)

275276277

272

274

The relationship between the total number of hours patched and the suppression score will be illustrated using a boxplot, rather than a scatterplot.

278279280

281

282

283

284

285

286

Patching adherence is categorized by the study coordinator as excellent, good, fair, or poor based on inspection of the patching calendar and discussion with the parent. This data will be tabulated for the 3-month visit, as will the reasons for any major deviations. Descriptive statistics and a boxplot for total number of hours patched as recorded with the ODM by level of patching adherence based on parent report will be obtained.

6 Association of Retinal Correspondence Testing to Other Outcomes

The relationship between retinal correspondence response and each of the following outcomes within each treatment group will be evaluated at 3 months:

287 288 289

290

291

293

294

295

296

- 1. Distance control score
- 2. Near control score
 - 3. Distance angle of deviation
- 292 4. Near angle of deviation
 - 5. Suppression Score (0=negligible, 1=mild, 2=moderate, 3=dense)
 - 6. Convergence fusional amplitudes
 - 7. Divergence fusional amplitudes
 - 8. Diplopia by parental assessment (dichotomized as in section 4.5)
 - 9. PedEyeQ score

Normal retinal correspondence will be defined as correspondence status marked "normal" both when aligned and tropic, while anomalous retinal correspondence will be defined as correspondence status marked "abnormal" when aligned or tropic (or both).

301 302 303

304

305

306

307

308

309

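### The wear-time dose-response is an unadjusted Spearman correlation; it should be conditioned on baseline and its outcome scale stated, because baseline control predicts change

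*Protocol*

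**What the plan says.** Protocol 1.6 lists among its open questions: "Is there a dose-response relationship (greater improvement with more actual patching" time). Protocol 7.8.1 plans to evaluate the "potential correlation between actual patch wear time in the FT patching group and the change" from baseline in ten outcomes, and adds: "A Spearman correlation coefficient and 95% confidence interval will be calculated for each" outcome. SAP 5 words it differently: "Scatterplots, with Spearman correlation coefficients and 95% confidence intervals, will be generated to illustrate the relationship between the total number of hours patched" and each listed outcome. Its list names the outcomes (distance control score, near control score and so on) without saying change. Neither document includes a baseline term, a partial correlation or a regression.

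On baseline, Protocol 7.3 reports from the IXT2 data that the correlation between baseline distance control and "change from baseline after 3 months was R=0.39 (95% CI, 0.27 to 0.48"). The sample size uses a lower value: "months, and a correlation of 0.30 between distance control score at baseline and change from" baseline. The primary ANCOVA adjusts for baseline distance control and baseline distance PACT. For exploratory comparisons of the randomized groups, SAP 4 states: "Treatment group differences and 95% CIs will be estimated using an ANCOVA model with adjustment for baseline level of the outcome".

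**The concern.** Hours worn are a post-randomization behaviour. Families of children with worse (or better) control may patch more, and randomization does not protect a comparison within one arm. Baseline also predicts the outcome. Part of this is built into the scale: under SAP 2 a child must enter with a mean of at least 2.0 and cannot score below 0, so a child starting at 2.0 can improve by at most 2 points and one starting at 5.0 by 5. Analysing change therefore does not remove baseline.

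If wear and baseline are related, the raw correlation mixes the two, and its direction of error depends on the scale. Where heavier wearers start worse, a correlation with change overstates the benefit of wear, and a correlation with the 3-month score understates it. Protocol 1.5 says the authors know of no earlier study of actual wear time in IXT, so this estimate may shape later work on patching dose.

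**Working it through.** Improvement is taken as positive throughout.

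**Inputs.** From Protocol 7.3, 34 completers per arm. This reproduces: SD 1.5×√(1−0.30²) = 1.431, difference 1.15, two-sided 5%, noncentral t with N−3 df gives power 0.904 at N = 68. SDs for baseline, 3-month score and change come from Table 1: 1.00, 1.23, 1.38 (patching) and 1.01, 1.35, 1.23 (observation).

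**Step 1: how strongly baseline predicts outcome.**

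r(baseline, improvement) = (s_b² + s_c² − s_f²)/(2·s_b·s_c)
- Patching: (1.00² + 1.38² − 1.23²)/(2×1.00×1.38) = 0.50
- Observation: (1.01² + 1.23² − 1.35²)/(2×1.01×1.23) = 0.29

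These bracket the stated 0.39.

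r(baseline, 3-month score) = (s_b² + s_f² − s_c²)/(2·s_b·s_f)
- Patching: 0.25
- Observation: 0.49

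**Step 2: assumed wear-baseline correlation ρ.** The documents give none; ±0.3 and ±0.5 are assumptions. With a baseline SD of 1.0, better- and poorer-wearing halves differ by 2√(2/π)·ρ = 1.596ρ, that is about 0.48 point at 0.3 and 0.80 point at 0.5.

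**Step 3: no true effect of wear, change scale.** The expected raw Spearman is (6/π)·arcsin(ρr/2). For ρ = 0.3 and r = 0.30 this is 0.086. Simulation at n = 34, with a Fisher-z 95% CI and variance 1.06/(n−3−k), where k is the number of conditioning variables, gives:

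| r(baseline, change) | ρ = ±0.3: bias; CI excludes zero | ρ = ±0.5: bias; CI excludes zero |
|---|---|---|
| 0.30 (planning) | 0.08; 7% | 0.14; about 12% |
| 0.39 (stated) | 0.11; 9% | 0.19 (formula only) |
| 0.50 (Table 1, patching) | 0.14; 11-12% | 0.23; 25-26% |

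The partial Spearman given baseline averages within about 0.01 of zero, and its CI excludes zero in about 4-5% of trials.

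**Step 4: 3-month-score scale.** With halves 0.5 point apart (ρ = 0.31) and heavier wearers worse at baseline, the expected raw correlation with no effect of wear is 0.07 (r = 0.25) to 0.15 (r = 0.49), pointing towards harm. On change the same imbalance points towards benefit.

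**Step 5: a true effect exists** (r = 0.39, n = 34).
- True partial correlation 0.4, change scale: the raw estimate averages 0.21 at ρ = −0.31 and 0.44 at ρ = +0.31; the partial averages 0.36-0.38.
- True 0.2: raw on change averages 0.17 at ρ = 0 and 0.05 at ρ = −0.31. It turns negative (−0.10) at ρ = −0.63, a 1.0-point difference between halves.
- True 0.1: raw on change averages −0.03 at ρ = −0.31.

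**Step 6: no wear-baseline association.** There is no bias. For a true partial correlation of 0.40 on change, the CI excludes zero in 46% (r = 0.50) to 54% (r = 0.30) of trials raw, and in about 57% adjusted.

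**The case against.** The case for leaving the plan alone is substantial.

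- **Status.** Protocol 7.8 classes the analysis as exploratory, SAP 5 uses the correlations to illustrate, and no test or decision hangs on them. Protocol 1.5 already warns that imperfect adherence limits dose-outcome interpretation. This stands: no primary, secondary or safety conclusion changes.
- **The key input is unknown.** No wear-baseline association is reported, and at zero there is no bias. The 0.50 comes from SDs on unequal samples (131 at baseline, 116 for change), in a trial of 3 hours per day with a single control measure; this trial averages three. This stands, and is why the range starts from the planning value of 0.30.
- **Precision.** At n = 34 the CI half-width is tanh(1.96×√(1.06/31)) = 0.35, larger than any bias tabulated above. That limits the harm, but a wide interval around a shifted centre is no reason to keep a shift that collected data can remove.
- **Limits of adjustment.** Conditioning on baseline leaves age, family motivation and stopping for poor response untouched. It also costs cases for fusional amplitudes, which Protocol 4.1 records as unable when exotropia is manifest.

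A reader might also infer that this is the one unadjusted analysis in a plan that otherwise always adjusts. The documents do not support that. SAP 4.2 compares fusional amplitudes by an unadjusted Wilcoxon test, and SAP 6 takes unadjusted mean differences between retinal-correspondence groups. The SAP 4 sentence on ANCOVA covers treatment-group differences only.

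**Conclusion.** The concern holds as a cheap improvement to an exploratory analysis. The planned estimate does not separate wear from baseline severity, and the two documents do not state the same outcome scale. With no true effect and n = 34, the raw Spearman with change is biased by about 0.08-0.14 at an assumed wear-baseline correlation of ±0.3 and 0.14-0.23 at ±0.5. The CI excludes zero in about 7-12% and 12-26% of trials, against about 5% for the partial Spearman. Without any such association, the gain is precision on change only.

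A reader might go further and infer that the planned analysis is likely to reverse a real dose-response. The figures do not support that. Imbalance can inflate or hide a true association, but reversal in expectation needs a weak one (about 0.1-0.2) together with a sizeable imbalance. A true partial correlation of 0.4 is reduced but keeps its sign at every imbalance examined.

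**What to change.** In Protocol 7.8.1 and SAP 5:

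- State whether each outcome enters as change from baseline or as the 3-month value.
- For distance and near control, distance and near angle, suppression and the PedEyeQ domains, report a partial Spearman correlation with 95% CI, conditioned on the baseline value of the same outcome, as the main dose-response estimate.
- Keep the raw Spearman coefficients and plots as description.
- For fusional amplitudes, report the partial correlation only in children with a measurable baseline, and give the n.
- Leave the symptom survey descriptive: SAP 4.3 tabulates items and defines no total score to condition on.
- Say in the text that wear time is not randomized and that other confounding remains.

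The cost is a few sentences, one degree of freedom per correlation and some lost amplitude cases. No new data are needed: Protocol 2.4 already collects these baseline measures.
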